The aim of this study is to test the classification accuracy and neural associations of a series of newly created neuropsychological assessment, which collectively form the computerised cognitive assessment for preclinical Alzheimer's disease (CoCoA-PAD).

2. Background and Rationale

Alzheimer's disease (AD) healthcare is on the verge of significant change. Healthcare providers can now diagnose people with pre-dementia AD (i.e., preclinical and prodromal AD), and new disease modifying medications can slow cognitive decline (see Jack Jr et al., 2024). Health services are now faced with the challenge of implementing these developments into clinical practice. NHS England and the National Dementia Team have developed an initial implementation strategy (Murdoch & Stewart, 2024). It states that diagnostic assessments will be delivered in newly commissioned neurology and neuropsychology clinics, and that the completion of a 'comprehensive cognitive assessment' is required to diagnose the AD clinical syndrome, and stage the disease severity.

While AD biomarker assessments, such as plasma and cerebral spinal fluid assessments, provide information on the presence of AD proteins (Amyloid and Tau), they are not predictive of future dementia, i.e., only 22% of 65-year-olds with preclinical AD biomarkers will develop Alzheimer's dementia in their lifetime (Brookmeyer & Abdalla, 2018). As such, the International Working Group (IWG) provide clear recommendations that the use of AD biomarkers in isolation in cognitive unimpaired older adults is not advisable and in fact may lead to harm (Dubois et al., 2024). In contrast, meta-analytic research has demonstrated that the combination of biomarkers and cognitive assessments improves predictive accuracy for future AD dementia to 73% (Parnetti et al., 2019). The IWG have proposed that a clinical-biological definition of AD is adopted into clinical practice (Dubois et al., 2024), and that the combination of plasma and sensitive cognitive markers of AD represent the most feasible strategy for a meaningful diagnosis of preclinical and prodromal AD (Vonk, 2025).

2.1. The Implementation of Cognitive Assessment Pathways

There are severe barriers to the implementation of comprehensive cognitive assessments for early AD into NHS practice. Most cognitive assessments are grossly insensitive to the early cognitive difficulties associated with AD and therefore not fit for purpose (Curiel Cid & Loewenstein, 2022). Indeed, large scale research including over 5,000 participants, identified that traditional cognitive assessments do not add any predictive accuracy above demographic factors and genetics, to determine the risk of preclinical AD (Liu et al., 2025). There are some notable exceptions (e.g., APICC & PACC, Langbaum et al., 2020; Bransby et al., 2019), but these rely on tests that can only be administered by practitioner psychologists, e.g., Logical Memory from Wechsler Memory Scales (WMS-IV). There is currently a national shortage of practitioner psychologists in the UK (NHS England, 2023). Two recent economic modelling studies demonstrate that the implementation of 'psychologist' delivered cognitive assessment onto early AD pathways would cost the NHS £4.2 billion to deliver (Mattke et al., 2024a), and without this investment, waiting lists would reach over 10 years by 2029 (Mattke et al., 2024b).

Therefore, the delivery of early AD cognitive assessment cannot be achieved by relying on existing cognitive tests or the existing workforce model. There is an urgent need for an implementation strategy for the delivery of large-scale cognitive assessment for early AD into the NHS, but there is no agreed upon strategy to achieve this.

Memory nurses are the largest staffing group in memory services and already have considerable experience administering and scoring brief cognitive *screening* tests, e.g., Montreal Cognitive Assessment (MoCA) and Addenbrooke's Cognitive Examination (ACE-III). Additionally, there is an impetus to increase the psychological workforce in the NHS through the delivery of the clinical associate psychologist (CAP) profession. In my opinion, the most realistic option of delivering comprehensive cognitive assessments at a large scale is to develop an assessment that can be reliably and robustly delivered by memory nurses and CAPs. Following consultation with memory nurses and neuropsychologists, there are two identified barriers to achieve this: 1) a lack of a standardised training protocol for non-practitioner psychologists on how to deliver cognitive assessments; and 2) a lack of available cognitive assessments that nurses and CAPs can use. This proposal seeks to co-design a nurse or non-practitioner psychologist administered cognitive assessment for preclinical AD, and co-produce a robust training protocol for nurses and allied health professionals to deliver cognitive assessments. If successful, this will contribute to the widespread delivery of early AD diagnosis and treatment through the NHS.

2.2. CoCoA-PAD Assessment

The long-term aim of the CoCoA-PAD project is to develop a validated assessment app which can be used in clinical practice. The CoCoA-PAD project seeks to collate the best experimental neuropsychological tests in the academic literature, and work with a team of stakeholders to co-produce these tests into a viable clinical assessment. In its current format, the CoCoA-PAD assessment is experimental, and none of the subtests have been validated previously. Therefore, the CoCoA-PAD assessment in its current form is not a medical device and does not require MHRA registration.

CoCoA-PAD is comprised of 16 standalone subtests, which are used to generate seven index scores (premorbid intelligence, memory, language and fluency, spatial processing, perceptual discriminability, cognitive control and performance validity). Figure 1 provides a list of the CoCoA-PAD subtests and the theorised hierarchical structure, and Appendix 1 provides a brief description of the subtest, the theoretical justification, and the reference test it is based on. CoCoA-PAD is designed based on an up-to-date understanding of the cognitive neurology of preclinical and prodromal Alzheimer's disease and the temporal ordering of cognitive difficulties (see Vogel et al., 2021). The assessments have been designed to assess the cognitive sequelae of preclinical AD, and the four preclinical syndromes identified by Vogel and colleagues (2021) (see figure 2).

CoCoA-PAD was designed to achieve two ambitions:

- *Maximise Efficiency.* CoCoA-PAD includes automatic and timed stimuli presentation, and automated scoring and psychometric calculations. This includes embedded machine learning approaches to maximise classification accuracy without the need for labour intensive scoring procedures. These steps ensure accuracy and reduce clinical time.
- *Maximise Clinical Value.* CoCoA-PAD incorporates many features that are designed to maximise clinical value, which do not exist in conventional neuropsychological assessments. This includes embedded measures of premorbid ability and performance validity, structured observational assessments of validity, functional cognitive disorder, and other cognitive difficulties, e.g., language.

2.3. Co-Production of CoCoA-PAD

The CoCoA-PAD assessment battery, and indeed all aspects of this research study, have been developed using a coproduction methodology, as outlined by the NIHR ([NIHR Guidance on co-producing a research project](#)). The co-production group consists of five older adults (including two with neurological conditions, one from an ethnic minority background, and one with educational deprivation), five assistant psychologists, two memory nurses, and seven clinical psychologists and neuropsychologists. The older adult coproduction group are involved in ensuring the assessment is well tolerated, the instructions are clear, that the test does not unduly discriminate against people with low computer literacy. The assistant psychologist group are involved in coproducing the usability of the assessment for the examiner. The memory nurses are coproducing the clinical observation checklists. The clinical psychologist and neuropsychology group are involved in coproducing the assessment governance and training requirements. All aspects of the assessment have been or are currently being co-produced.

CoCoA-PAD is delivered using Gorilla Experiment Builder 2.0 (EB2). Approximately half of the subtests (COBALT, MANE, SILT, Verbal Fluency, Connected Speech, Clock Drawing, and ALF) were initially developed and coproduced using a CoCoA-PAD web-based app, but due to costs associated with data storage, these tasks were transferred directly into Gorilla EB2. The remaining subtests were designed and co-produced using Gorilla EB2, an online platform for designing and running behavioural experiments. Gorilla Experiment Builder provides precise stimulus delivery, secure data collection, and easy remote access, making it well-suited for this research.

[figure not shown]

Figure 1. Proposed hierarchical structure of CoCoA-PAD

[figure not shown]

Figure 2. Mapping of CoCoA-PAD subtests onto the preclinical AD syndrome, and the four prodromal AD syndromes.

3. Objectives

3.1. Primary objective:

The long-term aim of this research is to develop a cognitive assessment which can be implemented into memory services and provides clinically meaningful information for healthcare staff. There are four primary research objectives, which stem from this ambition:

- i. To establish the diagnostic accuracy of the CoCoA-PAD subtests at distinguishing people with preclinical Alzheimer's disease (stages 1 and 2) from healthy controls.
- ii. To establish the diagnostic accuracy of the CoCoA-PAD subtests at distinguishing people with prodromal Alzheimer's disease (stage 3) from healthy controls.
- iii. To measure the relationship between CoCoA-PAD subtests and measures of neurodegeneration.
- iv. To test whether CoCoA-PAD subtests are sensitive at detecting cognitive deterioration over a one-year period.

3.2. Secondary objectives:

- i. To assess the usability of the assessment from both a service user and assessor perspective.
- ii. To determine the strength of the relationship between pTau-217 levels and cognitive assessment performance on the CoCoA-PAD subtests
- iii. To establish the diagnostic accuracy of the CoCoA-PAD subtests at distinguishing people with prodromal Alzheimer's disease against those with non-AD related Mild Cognitive Impairment (MCI).

4. Study Design and Sampling Method

This research study is comprised of three sub-studies. Although each study includes a cohort of the same participants, each sub-study has its own sampling procedure and research design, which I have outlined below:

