4.1. Study 1. Evaluating the Diagnostic Accuracy of CoCoA-PAD subtests

Participants

A total of 120 participants will be recruited: 60 participants with subjective cognitive decline (SCD) and 60 participants with mild cognitive impairment (MCI). Participants will be classified post-recruitment into four distinct diagnostic groups: healthy controls, preclinical AD, prodromal AD, and non-AD related MCI. Figure 3 provides a flow of the estimated frequencies of each diagnostic group within the sample.

Sampling

This study will use a stratified sampling approach with post-hoc diagnostic classification. A prospective quasi-experimental between-group research design will be employed.

A stratified sampling approach will ensure that key demographic information, including years of education and ethnicity, will match national population demographics of the UK. 2021 census data revealed that 6% of 70–74-year-olds in the UK are from non-white ethnic minority backgrounds. However, given that people from minority ethnic backgrounds are significantly more likely to have dementia but less likely to receive a diagnosis (Okeoghene Ighomereho, 2025), for the purpose of this study, the stratified sampling target will be inflated to 10%.

Similarly, 2021 census data has mapped the educational attainment of the UK population. No age-specific education attainment values were published, but regional values have been published, and Plymouth demographics have been selected for this study. This is based on coastal communities having higher rates of dementia, lower rates of diagnosis, and significant social inequalities which often exclude them from research (Alzheimer’s Research UK, 2024). This study will replicate educational attainment values, with provision for 5% variation in the recruitment to each education level – see Table 1.

Table 1. Educational Attainment and Stratified Sampling Target

Educational Attainment	Plymouth Demographics	CoCoA-PAD Recruitment Target Range
No Qualification	17%	14-26
Level 1 (O level any grade)	10%	6-18
Level 2 (O levels passes)	14%	11-23
Apprenticeship	6%	1-13
Level 3 (A level equivalent)	17%	14-26
Level 4 (3 rd level qualifications)	34%	35-47
Other	2%	0-8

Procedure

Participants will be recruited and classified post-recruitment into diagnostic groups on the basis of AD biomarker results (pTau-217) and performance on the M-ACE, using a cut-off score of 20 for MCI (Potts et al., 2022).

Measures

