Performance on the CoCoA-PAD subtests will be compared across diagnostic groups. Scores will be compared across the different diagnostic categories, i.e., non-AD subjective cognitive decline (i.e., healthy controls) versus preclinical AD, versus prodromal AD.

[figure not shown]

Figure 3. Estimated post-diagnostic participant numbers for Study 1

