5.5. Participant Screening Criteria

Subjective Cognitive Decline

Subjective cognitive decline (SCD) is a research descriptor used to refer to people who believe that their cognitive functioning has deteriorated despite performing in the 'normal' range on objective measures of cognitive functioning. People with SCD are at increased risk of developing dementia (Glodzik-Sobanska et al., 2007), and therefore SCD is considered a potential early clinical manifestation of Alzheimer's disease. Jessen and colleagues (2014) developed a widely used research criteria to define SCD. It includes:

1. Self-experienced persistent decline in cognitive capacity in comparison with a previously normal status and unrelated to an acute event.
2. Normal age, gender, and education adjusted performance on standardised cognitive tests, which are used to classify mild cognitive impairment (MCI) or prodromal AD.

Exclusion criteria for SCD include mild cognitive impairment, prodromal AD, or dementia; that difficulties can be explained by a psychiatric or neurologic disease (apart from AD), medical disorder, medication, or substance use.

In addition, the authors also provide guidance on the criteria for SCD *plus*, which increases the likelihood of preclinical AD, and includes:

- Subjective decline in memory, rather than other domains of cognition

- Onset of SCD within the last 5 years
- Age at onset of SCD ≥ 60
- Concerns (worries) associated with SCD
- Feeling of worse performance than others of the same age group

Mild Cognitive Impairment

Mild Cognitive Impairment (MCI) is a descriptor used to refer to people who report experiencing a decline in cognitive functioning *and* demonstrate cognitive impairment on objective testing. It is thought to be a transitional phase between normal aging and dementia. Albert and colleagues (2011) on behalf of the National Institute on Aging - Alzheimer's Association (NIA-AA) developed diagnostic guidelines for research. They include:

- Cognitive concern reflecting a change in cognition reported by patient or informant or clinician (i.e., historical or observed evidence of decline over time)
- Objective evidence of Impairment in one or more cognitive domains, typically including memory (i.e., formal or bedside testing to establish level of cognitive function in multiple domains)
- Preservation of independence in functional abilities
- Not demented.

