With regards to how cognitive impairment is classified, the authors state that 'cognitive tests for individuals with MCI are typically 1 to 1.5 standard deviations below the mean for their age and education matched peers on culturally appropriate normative data'.

Table 3 provides a breakdown of the specific inclusion and exclusion criteria used in the CoCoA-PAD study.

Table 3. Recruitment Criteria for Subjective Cognitive Decline and Mild Cognitive Impairment

Subjective Cognitive Decline	
Inclusion Criteria	Exclusion Criteria

 • >3.38 on IQCODE Self-Report items 1-7 (PROTECT) OR 
 • ≥ 4 on SCD-Q9 (non-Protect) AND 
 • Age ≥ 65 years • Onset of SCD within the last 5 years • English as a first language • Normal demographically adjusted performance on standardised cognitive tests • Specific Race and Education (using stratified sampling approach) 	
 • Cognitive impairment, i.e., performance ≥ 1 SD below demographically adjusted norms (PROTECT) OR 
 • ≤ 17 on the telephone MoCA (non-PROTECT) AND 
 • Lacks mental capacity to consent to research • Diagnosis of dementia • Sensory impairment that cannot be corrected for with sensory aids, e.g., blindness. • Previous neurological injury (stroke, traumatic brain injury, severe epilepsy, brain tumour)

	
 • Other neurodegenerative syndrome (e.g., Parkinson's disease, multiple sclerosis, etc) • Diagnosis of learning disability • Severe depression (PHQ-9\geq15 OR score \geq1 on PHQ-9 suicide question) • Current severe psychiatric disorder (bipolar disorder, schizophrenia, or psychotic disorders) • Current drug or alcohol abuse • Untreated diagnosis of sleep apnoea.
Mild Cognitive Impairment	
Inclusion Criteria	Exclusion Criteria

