6.2. Measures included in the Research Appointment

Demographic Questionnaire

A brief demographic questionnaire will be used to collect information regarding participants date of birth, age, gender, ethnicity, educational history and occupational history. The demographic questionnaire will only be administered in the time 1 assessment.

Health History

Participants will be asked to identify whether they experience any comorbid health related difficulties, including sleep apnoea, arthritis, motor problems, sensory loss, etc. Additionally, participants will be asked to list their current medications. At the follow up assessment, participants will be asked whether their health history has changed in the past year.

pTau-217

Phosphorylated tau-217 (p-tau217)—tau phosphorylated at threonine-217—is a blood biomarker of Alzheimer’s-type tauopathy downstream of amyloid- β pathology. Multiple studies show that plasma p-tau217 identifies biological Alzheimer’s disease with diagnostic accuracy comparable to established CSF tests (and sometimes similar or superior in head-to-head evaluations), including for A β -PET and tau-PET status (Barthélemy et al., 2024; Martínez-Dubarbíe et al., 2025). Levels become abnormal early and increase with disease burden, supporting its potential use for biological staging from at least stage 2 onward and tracking longitudinal change (Mattsson-Carlsson et al., 2020). Research has demonstrated that the combination of SCD+ criteria and a positive plasma pTau-217 biomarker result are effective at classifying stage-2 of the AD spectrum (Mengel et al., 2025).

In the 2024 NIA-AA revised criteria, p-tau217 was classified as a Core-1 biomarkers that can establish the biological diagnosis of AD across the disease continuum; however, while cut-offs exist, routine clinical use is not yet established and implementation remains guidance-led and setting-dependent (Jack et al., 2024; Palmqvist et al., 2025).

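### Primary objective i claims accuracy for preclinical AD stages 1 and 2, but every entry route requires subjective decline and no rule separates stage 1 from stage 2

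*Protocol*

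**What the plan says.** Section 3.1, objective i, is to establish how well the subtests separate preclinical Alzheimer's disease ("stages 1 and 2) from healthy controls"). Objective ii does the same for "prodromal Alzheimer's disease (stage 3) from healthy controls".

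Section 4.1 recruits "60 participants with subjective cognitive decline (SCD) and 60 participants with mild cognitive impairment (MCI". There is no arm of people without complaints. After recruitment, participants are grouped by pTau-217 result and by M-ACE score, with a cut-off of 20 for MCI. The control group is "non-AD subjective cognitive decline (i.e., healthy controls").

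Section 5.5 describes SCD as "Self-experienced persistent decline in cognitive capacity in comparison with a previously normal status and unrelated to an acute event". Table 3 requires a self-report IQCODE score above 3.38 (PROTECT) or an SCD-Q9 score of at least 4 (other sources) for the SCD arm. The MCI arm uses the same thresholds with objective impairment, or a memory-clinic MCI diagnosis. Both arms add "Onset of SCD within the last 5 years" as a criterion that must also be met.

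On staging, section 6.2 says that the SCD plus criteria combined with a positive plasma pTau-217 "are effective at classifying stage-2 of the AD spectrum".

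**The concern.** The objective names two preclinical stages, while the entry criteria appear to admit only people who already report decline. If stage 1 is the complaint-free, biomarker-positive stage, the trial has no way to enrol it. If stage 1 means something else, the protocol does not say what, and pTau-217 with M-ACE cannot separate it from stage 2.

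This is the first of four primary objectives. The ROC curves, AUCs, sensitivities and specificities in section 11.4 will be read against it. Section 7.8 says that insensitive tests will be dropped on the strength of the results, and section 7.9 makes commercialisation conditional on the accuracy achieved. An accuracy figure labelled as covering stage 1 would extend to people whom the design does not set out to observe, and the direction of the resulting error is unknown.

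**Working it through.** **1. Sample size: does the point touch it?** Section 11.3 uses a fixed one-way ANOVA with f = 0.33, k = 3, alpha = 0.05 and power 0.8, and states a minimum of 90. With the noncentral F distribution, lambda = N × f² and degrees of freedom are 2 and N − 3.
- N = 90: lambda = 90 × 0.1089 = 9.80, power 0.793.
- The smallest N that reaches 0.80 is 92, where power is 0.802.
- Projected N = 36 + 18 + 40 = 94: lambda = 10.24, power 0.811.

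The stated figure reproduces to within two participants. None of its inputs depends on a stage label, so the point leaves it unchanged.

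**2. Is there an entry route without subjective decline?** The rest of the check concerns eligibility. Table 3 gives 2 + 3 = 5 routes:

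| Arm | Route | Self-report threshold | SCD onset within 5 years |
|---|---|---|---|
| SCD | PROTECT | IQCODE > 3.38 | required |
| SCD | non-PROTECT | SCD-Q9 ≥ 4 | required |
| MCI | PROTECT | IQCODE > 3.38 | required |
| MCI | non-PROTECT | SCD-Q9 ≥ 4 | required |
| MCI | memory-clinic diagnosis | none | required |

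No route (0 of 5) is open to a person without subjective decline. The memory-clinic route has no questionnaire threshold but still carries the onset criterion. Someone recruited as MCI who scores above the M-ACE cut-off may be placed in the preclinical or control group, but entered under the same criterion. Section 7.1 agrees: it describes the target population as people who report cognitive decline.

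**3. Could the grouping recover stage 1?** Section 4.1 uses two variables. M-ACE separates MCI from not-MCI, and pTau-217 separates AD from non-AD. Among those above the M-ACE cut-off this gives two cells, biomarker-positive and biomarker-negative. Nothing divides the positive cell into stages 1 and 2.

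**4. What does the protocol say stage 2 is?** Section 6.2 ties it to the SCD plus criteria with positive pTau-217. Section 5.5 lists five SCD plus features. Table 3 requires age of at least 65 and onset within 5 years, so onset falls at about 65 − 5 = 60 or later. Enrolees therefore meet two of the five: recent onset, and onset at 60 or above. Memory-specific decline, worry, and feeling worse than peers are not required. The enrolled preclinical group is thus broader than the group that section 6.2 links to stage 2.

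**The case against.** The strongest reply is that the protocol never defines stage 1, so its absence cannot be proved from the text. That stands, and the meaning used here is an inference. It does not rescue the objective, because under any other meaning there is still no rule to separate the two stages.

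A reader might go further and infer that the protocol classes every pTau-217-positive person with SCD as stage 2. It does not: section 6.2 refers to SCD plus, and Table 3 asks for only part of that. Section 6.1 also uses stage 2 for difficulties detected by the FLAME battery, whereas SCD entry requires normal test performance.

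A reader might also state flatly that 0 of 120 participants will be stage 1. That count rests on the inferred definition. In addition, PROTECT entrants qualify on earlier IQCODE scores and complete the SCD-Q9 at the research appointment (sections 6.1 and 6.6), so some may score below 4 that day. That is a second measurement which section 4.1 does not use for grouping; it creates neither a complaint-free entry route nor a stage 1 rule.

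Finally, a reader might say that symptomatic controls are being passed off as healthy. The documents do not support this. Sections 4.1 and 11.3 both openly define the controls as people with subjective problems and no AD biomarker evidence. What remains is that objective i omits that qualifier.

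**Conclusion.** Objective i is wrong as written. Its stage 1 claim cannot be supported by the population that Table 3 admits or by the classification in section 4.1. The firm result is that none of the five entry routes is open to a complaint-free person, and that there is no stage 1 versus stage 2 rule. The data will support a comparison of about 18 pTau-217-positive with 36 pTau-217-negative people (section 11.3 projections), all of whom entered with subjective decline and score above the M-ACE cut-off.

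The conclusion assumes that Table 3 is applied as written. Equating stage 1 with biomarker positivity without complaints is inferred, but the verdict does not depend on it alone. Sections 4.1 and 11.3 carry no stage label and are not in error, and the sample size is unaffected.

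**What to change.** Change objective i only. Remove stage 1 and name the comparison that the design can make, for example: *diagnostic accuracy of the CoCoA-PAD subtests for pTau-217-positive versus pTau-217-negative people with subjective cognitive decline who score above the M-ACE cut-off for MCI*. Carry over the control definition from sections 4.1 and 11.3, so that the objective itself shows that the controls have subjective decline.

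Do not relabel the whole preclinical group as stage 2 unless the protocol first defines that stage for SCD as enrolled; section 6.2 speaks only of SCD plus.

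The cost is wording and a narrower stated claim. Recruitment, procedures, grouping, analysis and the sample size stay as they are.
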